10.3 VITAL SIGNS

Descriptive statistics for vital signs (sitting systolic and diastolic blood pressure, pulse rate, respiration rate, temperature, height, weight, BMI, height percentile, weight percentile, and BMI percentile) and their changes from baseline values at each visit and at the end of study will be presented by treatment group. Height, weight and BMI z-scores will be calculated based on Centers for Disease Control (CDC) growth charts. Only subjects with available baseline and at least 1 postbaseline assessment will be included in the summary.

Vital sign values will be considered PCS if they meet both the observed-value criteria and the change-from-baseline criteria listed in Table 10.3–1. The number and percentage of subjects with PCS postbaseline values will be tabulated by treatment group separately. The percentages will be calculated relative to the number of subjects with available baseline and at least 1 postbaseline assessment. The numerator will be the total number of subjects with available baseline values and at least 1 PCS postbaseline value. A supportive listing of subjects with PCS postbaseline values will be provided, including the SID number, study center number, and baseline and all postbaseline (including non-PCS) values.

In addition, a listing of all AEs that occurred in subjects who had PCS postbaseline vital sign values will be provided.

Table 10.3–1. Criteria for Potentially Clinically Significant Vital Signs

		Criteria ^a				
Parameter	Flag	Observ	ed Value	Change From Pageline		
		Age 7-11	Age 12-17	Change From Baseline		
	High	≥ 125	≥ 140	Increase of ≥ 20		

Page 35 of 53

Sitting systolic blood pressure, mm Hg	Low	≤ 85	≤ 90	Decrease of ≥ 20
Sitting diastolic blood	High	≥ 90	≥ 95	Increase of ≥ 15
pressure, mm Hg	Low	≤ 40	≤ 50	Decrease of ≥ 15
C'44'	High	≥ 130	≥ 110	Increase of ≥ 15
Sitting pulse rate, bpm	Low	≤ 55	≤ 45	Decrease of ≥ 15
Waisht les	High	_	_	> 2 deviations above the age-gender mean weight
Weight, kg	Low	_	_	> 2 deviations below the age-gender mean weight

a A post-baseline value is considered potentially clinically significant if it meets both the observed-value and the change-from-baseline criteria.

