11.6.1.2 Vital Signs

Descriptive statistics for vital signs (ie, blood pressure, pulse rate, temperature, respiration rate, height, weight, BMI, height percentile, weight percentile, and BMI percentile) and changes from baseline values at each visit and at end of study will be presented by treatment group. Height, weight, and BMI z-scores will be calculated based on CDC growth charts.

Vital sign values will be PCS if they meet both the observed-value criteria and the change from baseline-value criteria. The criteria for PCS vital sign values will be detailed in the SAP. The percentages will be calculated relative to the number of subjects with baseline values and at least one postbaseline assessment. The numerator will be the total number of subjects with available baseline values and at least one PCS postbaseline value. A supportive listing of subjects with PCS postbaseline values will be provided, including the subject identification (SID) number, study center number, and

CONFIDENTIAL

baseline and postbaseline values. A listing of all AEs for subjects with PCS vital sign values will also be provided.

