10.2 CLINICAL LABORATORY PARAMETERS

Descriptive statistics for clinical laboratory values (in SI units) and changes from the baseline values at each assessment time point (including the end of the double-blind acute treatment period) will be presented by treatment group for the following laboratory parameters:

Hematology: Hemoglobin, hematocrit, white blood cell count (total and

differential), red blood cell count, platelet count, mean cell volume, mean cell hemoglobin (MCH), and MCH concentration.

Chemistry: Creatinine, urea (or blood urea nitrogen), aspartate transferase,

alanine transferase, gamma glutamyltransferase, alkaline phosphatase, lactate dehydrogenase, total bilirubin, albumin, total protein, sodium, potassium, chloride, glucose, uric acid, calcium,

phosphorus, thyroid-stimulating hormone, T3, and T4.

Urinalysis: pH, glucose, ketones, blood, protein, and microscopy.

Clinical laboratory test values will be considered potentially clinically significant (PCS) if they meet either the lower-limit or higher-limit PCS criteria listed in Table 10.2–1. The number and percentage of subjects who have PCS post-baseline clinical laboratory values will be tabulated by treatment group. The percentages will be calculated relative to the number of subjects with available non-PCS baseline values and at least 1 postbaseline assessment. The numerator will be the total number of subjects with available non-PCS baseline values and at least 1 PCS post-baseline value. A supportive listing of subjects with PCS post-baseline values will be provided, including the subject identification (SID) number, study center number, and baseline and all post-baseline (including non-PCS) values.

In addition, a listing of all AEs that occurred in subjects who had PCS post-baseline clinical laboratory values will be provided.

Table 10.2–1. Criteria for Potentially Clinically Significant Laboratory Values

Parameter	SI Unit	Lower Limit	Higher Limit
HEMATOLOGY			
Basophils	%		> 6
Eosinophils	%		> 10
Hematocrit	1.0	< 0.9 × LLN	
Hemoglobin	g/L	< 0.9 × LLN	
Lymphocytes	%	< 10	> 60
Monocytes	%	_	> 20
Neutrophils	%	< 30	> 90
Platelet count	× 10 ⁹ /L	≤ 75	≥ 700

Page 33 of 53

White blood cell count	$\times 10^9/L$	≤ 2.5	≥ 15
CHEMISTRY			
Albumin	g/L	< 0.9 × LLN	> 1.1 × ULN
Alkaline phosphatase	U/L	_	\geq 3 × ULN
Alanine	U/L		\geq 3 × ULN
aminotransferase	U/L	_	≥ 3 ^ OLN
Aspartate	U/L		\geq 3 × ULN
aminotransferase			_
Bicarbonate	mmol/L	< 0.9 × LLN	> 1.1 × ULN

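### The weight row of SAP Table 10.3–1 does not fit the two-criterion PCS rule and, read as a position, mixes children already beyond 2 SD at baseline with new cases

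*SAP*

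**What the plan says.** The rule appears three times. Protocol 11.6.1.2: "Vital sign values will be PCS if they meet both the observed-value criteria and the change from baseline-value criteria". That section leaves the limits themselves to the SAP. SAP 10.3 repeats it: "Vital sign values will be considered PCS if they meet both the observed-value criteria and the change-from-baseline criteria". Footnote a to SAP Table 10.3–1 repeats it again: "A post-baseline value is considered potentially clinically significant if it meets both the observed-value and the change-from-baseline criteria".

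In that table, blood pressure and pulse have age-specific observed limits and a numeric change. Weight has only dashes in both observed-value columns. Its change column holds "> 2 deviations above the age-gender mean weight" for the high flag and "> 2 deviations below the age-gender mean weight" for the low flag.

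For the vital-sign PCS denominator, SAP 10.3 says: "The percentages will be calculated relative to the number of subjects with available baseline and at least 1 postbaseline assessment". For the numerator: "The numerator will be the total number of subjects with available baseline values and at least 1 PCS postbaseline value". The laboratory rule in SAP 10.2 is narrower: "The numerator will be the total number of subjects with available non-PCS baseline values and at least 1 PCS post-baseline value". SAP 10.4 applies the same non-PCS-baseline restriction to ECG values.

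Elsewhere, SAP 10.3 plans descriptive changes in weight, BMI and their percentiles by arm, computes weight z-scores from the CDC charts, and lists all values of every PCS subject. SAP 16.3 lets every post-baseline assessment count toward PCS. Inclusion criterion 14 limits BMI-for-age to the 3rd to 97th percentile and sets a 20 kg minimum. It sets no weight-for-age limit.

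**The concern.** The two-part rule exists so that a PCS flag means an extreme value that was not simply there all along. For blood pressure and pulse, the change limit does that work. For laboratory and ECG values, the non-PCS-baseline restriction does it. Weight has neither: its change cell is not a change, and the vital-sign counts accept any available baseline.

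Two programmers could therefore build different tables from this row. The most natural working interpretation treats the dash as no restriction and the cell as a position. On that interpretation, a child at z = 2.3 before and after treatment is flagged. The incidence of vital-sign PCS values is a named safety endpoint and the protocol lists weight among the vital signs, so the row will be reported. With so few flags, a baseline imbalance of one or two children could pass for a difference between arms, or cover one.

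**Working it through.** The plan gives no figure for this row, so there is nothing to reproduce. The check has two parts.

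**1. The row against its own rule.** There are three ways to read it:

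- *Literal, both criteria required.* One criterion is blank and the other is not a change. No value can be tested.
- *Position, dash meaning no restriction.* PCS if post-baseline weight z > 2 (or < −2). Baseline does not enter, so stable outliers count.
- *Change of more than 2 SD.* If the SD of the 8-week change in weight z is 0.1 to 0.3 (assumed), this needs a move of 2/0.3 = 6.7 to 2/0.1 = 20 SDs of change. It would practically never occur.

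No reading gives a usable count of new cases.

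**2. Size under the position reading.**

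Inputs from the documents: 128 per arm (protocol 8.3.1); BMI-for-age within the 3rd to 97th percentile, so c = Φ⁻¹(0.97) = 1.88 and P(|B| < c) = 0.94 (protocol 8.3.2).

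Assumptions not in the documents: weight z (W) is standard normal before the BMI limit; its correlation ρ with BMI z (B) is 0.6 to 0.9; the SD τ of the 8-week change in weight z is 0.1 to 0.3; there is one post-baseline reading. The 20 kg minimum is not modelled; it can only reduce the low tail.

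*Already beyond +2 SD at baseline:*

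P(W > 2 given |B| < c) = (1/0.94) ∫ from 2 to ∞ of φ(w) [Φ((c − ρw)/√(1 − ρ²)) − Φ((−c − ρw)/√(1 − ρ²))] dw

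- ρ = 0.6: 1.7%, or 2.2 per 128
- ρ = 0.7: 1.5%, or 1.9 per 128
- ρ = 0.8: 1.2%, or 1.5 per 128
- ρ = 0.9: 0.8%, or 1.0 per 128

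The low tail is symmetric. With no BMI limit the figure would be 1 − Φ(2) = 2.3% per tail.

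*Post-baseline flags:* W′ = W + d + e, with e normal with SD τ and d the drug shift. The share already high at baseline is P(W > 2 and W′ > 2) / P(W′ > 2). With d = 0:

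- High flags per arm run from 0.84% × 128 = 1.1 (ρ = 0.9, τ = 0.1) to 2.20% × 128 = 2.8 (ρ = 0.6, τ = 0.3).
- The share already high runs from about 88% (ρ = 0.6, τ = 0.1) down to about 42% (ρ = 0.9, τ = 0.3).
- New high flags number about 0.2 to 1.1 per arm.

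*What a drug effect does* (ρ = 0.7, τ = 0.2, d = +0.1 z):

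- As written, the high-flag rate goes from 1.70% (2.18 flags) to 2.22% (2.84 flags), a ratio of 2.22/1.70 = 1.31. Of the 2.84 flags, 61% were high at baseline.
- New crossings only: 0.60 to 1.11 flags, a ratio of 1.11/0.60 = 1.85.
- Difference over √(sum of counts): 0.66/√5.02, about 0.3, against 0.51/√1.71, about 0.4.

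The effect remains visible in the position count but is weaker against its background.

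**The case against.** A reader might infer that the weight count says nothing about the drug, or shows only who was enrolled. The documents do not support that. Arms are randomized and new crossings are counted alongside old ones. In the example above, the rate still moves from 1.70% to 2.22%.

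A reader might also take the unselected tail, 2 × 2.275% = 4.55%, or about 5.8 of 128, as the number flagged from the start. That ignores the BMI entry limit and adds two flags that the table keeps apart. With the limit, the total over both tails is about 2.0 to 4.4.

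Other points on that side also stand:

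- Weight and percentile changes by arm are summarized separately, and the PCS listing shows baseline values, so a stable outlier can be recognized.
- The protocol itself sets a wider denominator for vital signs than for laboratory and ECG values. For blood pressure and pulse this does no harm, because their change limit removes stable outliers. The gap is confined to weight.
- Since the row is strictly not evaluable, bias is not demonstrated. It follows only if the row is programmed as a position.
- Moving the limit to another column would not by itself satisfy the both-criteria rule, and a new denominator departs from protocol 11.6.1.2.

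None of this makes the row usable as printed. The listing and the change summaries help a reader look behind the incidence figure but do not correct it.

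**Conclusion.** The point holds in limited form. The weight row contradicts the rule stated in SAP 10.3, footnote a and protocol 11.6.1.2. Strictly read it cannot be evaluated; read as a position, it mixes children beyond 2 SD at baseline with new cases and dilutes any drug effect in the PCS incidence table. The contradiction rests on the text alone. The size, 1.0 to 2.2 baseline outliers per tail per arm making up roughly 42% to 88% of high flags when there is no drug effect, rests on the assumed normal weight z, the correlation range and the change SD, and should be quoted only as an illustration. The weight and percentile summaries, the PCS listing and the primary analysis are unaffected. This is a minor correction that is worth making because it costs so little.

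**What to change.** In SAP Table 10.3–1, keep the sponsor's ±2 SD limits and move them to the observed-value column. For weight only, restrict numerator and denominator to subjects within ±2 SD at baseline, and count those who cross a limit afterwards, as SAP 10.2 and 10.4 already do for laboratory and ECG values. Add to footnote a that for weight this crossing takes the place of the separate change criterion; otherwise the row would still fail the both-criteria rule. Record the departure from protocol 11.6.1.2 in SAP 17.0, which at present admits only one change, on weight and height z-scores in the demographic summary.

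No new clinical threshold and no new data are needed, since weight z-scores are already computed. The cost is one table row, one footnote sentence and one entry in 17.0. The weight denominator falls by about 2.0 to 4.4 per arm under the assumptions above, to roughly 124 to 126 of 128 before missing data. Few events will remain, about 0.2 to 1.1 new high flags per arm without a drug effect, so the row will be clean but sparse, and the change summaries stay the main evidence on weight.

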10.4 ELECTROCARDIOGRAM

Descriptive statistics for ECG parameters (heart rate, PR interval, QRS interval, RR interval, QT interval, and QTc interval) at baseline and changes from baseline values at each assessment time point will be presented by treatment group. The QTc interval is calculated using both the Bazett (QTcB = QT/(RR) $\frac{1}{2}$) and Fridericia (QTcF = QT/(RR) $\frac{1}{3}$) corrections. Only subjects with available baseline and at least 1 postbaseline assessment will be included in the summary.

Electrocardiographic parameter values are considered PCS if they meet or exceed the higher-limit PCS criteria listed in Table 10.4–1. The number and percentage of subjects with PCS postbaseline ECG values will be tabulated by treatment group. The percentages will be calculated relative to the number of subjects with available non-PCS baseline values and at least 1 postbaseline assessment. The numerator is the total number of subjects with available non-PCS baseline values and at least 1 PCS postbaseline value. A supportive listing of subjects with PCS postbaseline values will be provided, including the SID number, study center number, baseline, and all postbaseline (including non-PCS) values.

Table 10.4–1. Criteria for Potentially Clinically Significant Electrocardiographic Parameters

Parameter	Unit	Higher Limit
QRS interval	msec	≥ 150
PR interval	msec	≥ 250
QTcB	msec	> 460
QTcF	msec	> 450

QTcB = QT interval corrected for heart rate using the Bazett formula (QTcB = QT/(RR) $^{1/2}$); QTcF = QT interval corrected for heart rate using the Fridericia formula (QTcF = QT/(RR) $^{1/2}$).

bpm = beats per minute kg = kilogram, mmHg = millimeters of mercury hemoglobin.

Page 36 of 53

In addition, a listing of all AEs that occurred in subjects who had postbaseline PCS ECG values will be provided.

A listing of subjects with postbaseline clinically significant ECG abnormalities, as reported by the investigator or by the central cardiologist, will also be provided.

The number and percentage of subjects with an increase > 30 msec but ≤ 60 msec, and with an increase > 60 msec in QTcB or QTcF will be tabulated. A supportive listing of subjects with postbaseline QTcB or QTcF increases > 30 msec will be provided, including the SID number, study center number, and all QTcB and QTcF values (including changes from baseline). A listing of all AEs for subjects with postbaseline QTcB or QTcF increases > 30 msec will also be provided.

Shift tables from baseline to the end of double-blind acute treatment period in the Investigator's overall interpretation of the ECG and the central reader's overall interpretation will be presented separately by treatment group for the following categories: normal; abnormal, not clinically significant; abnormal, clinically significant.

10.5 COLUMBIA-SUICIDE SEVERITY RATING SCALE

For the C-SSRS, the number and percentage of subjects with any suicidal ideation or suicidal behavior will be presented by treatment group, separately for the lifetime history, the double-blind acute treatment period and the double-blind down-taper period. The distribution of responses for the most severe suicidal ideation and suicidal behavior will be summarized by treatment group, separately for the lifetime history, the double-blind acute treatment period, and the double-blind down-taper period. Supportive listings will be provided and will include the SID number, treatment group, visit number, lifetime history, and postbaseline values for each subject. Intensity of ideation, suicidal behavior type, and lethality of suicidal behavior will also be included in these listings.

SAP SCT-MD-60 Allergan

Page 37 of 53

